#### **4.1.1 Treatment Duration**

Subjects may continue treatment with APR-548 and azacitidine until disease progression, development of other unacceptable toxicity, confirmed pregnancy, HSCT, death, withdrawal of consent, or study termination, whichever occurs first. Subjects who experience disease progression per the applicable response criteria who are, in the opinion of the investigator, benefiting from treatment, may be allowed to continue on study drug with approval of the Medical Monitor.

Following discontinuation of study drug, subjects are to attend a follow-up visit 28 days after the last dose of study drug for final assessments. When study drug is withheld from a subject in order to resolve a toxicity and the subject does not subsequently restart treatment, end of treatment is defined as the date when the study drug was first held. Subjects should proceed with end of treatment assessments, safety, and survival follow-up. If the decision to not restart study treatment comes outside of the 28-day safety follow-up window, the subject should have an End of Treatment visit and proceed with survival follow-up.

Subjects who achieve an adequate response to treatment with APR-548 and meet other criteria required to undergo HSCT may proceed to HSCT after discontinuation of APR-548. If a subject proceeds to HSCT, evaluation of the extent of disease, response to treatment, and any new antineoplastic therapies will be collected at least monthly as long as the subject remains in remission and assessed as part of the study until relapse, death, withdrawal of

consent, loss to follow-up, or end of study, whichever comes first. If a subject discontinues APR-548 to undergo HSCT, but is then deemed ineligible for HSCT, the subject may restart APR-548 with Medical Monitor approval.

All subjects that enter survival follow-up will be contacted every two months for assessment of survival status and new antineoplastic therapies. Please see Section [6.9](#) for details on long-term follow-up.

## 4.2 End of Study

The end of the study is defined as the date of the last visit of the last subject undergoing the trial.

## 4.3 Drug Products

### 4.3.1 APR-548

### 4.3.2 Azacitidine

*Chemical Name:* 4-amino-1- $\beta$ -D-ribofuranosyl-s-triazin-2(1H)-one.

*Formulation, preparation, storage and stability:* Please see commercial package insert approved by regulatory agencies.

*Route of Administration:* s.c. injection or i.v. infusion administered s.c. or i.v. for 7 consecutive days (Days 1-7). S.c. route is preferred but will allow for i.v. at the investigator's discretion.

However, the same route should be maintained over the 7-day treatment period (whichever route of administration is used on Day 1, the same route should be followed on all other days). On the days of concomitant APR-548 administration, azacitidine will be administered 1 hour ( $\pm 15$  min) after APR-548 intake. Missed doses, such as for a weekend or holiday, for any reason but toxicity may, at the investigator's decision, be replaced by adding an additional dosing day for azacitidine so that the subject receives the total 7 days of treatment per cycle. If the azacitidine dose interruption is  $>3$  days, discuss with the Medical Monitor.

#### **4.4 Duration of Therapy**

Subjects may remain on study treatment to the end of the trial while deriving clinical benefit, unless unacceptable toxicity, death, or subject withdrawal. Subjects may remain on study treatment after disease progression if they are continuing to derive clinical benefit in the opinion of the investigator.

#### **4.5 Trial Discontinuation**

The Sponsor may terminate this study prematurely. Written notification of the termination is required. Conditions that may warrant termination include, but are not limited to:

- The discovery of an unexpected, significant, or unacceptable risk to the subjects enrolled in the study.
- Failure of the investigator to enter subjects at an acceptable rate.
- Insufficient adherence to protocol requirements (non-compliance).
- Lack of evaluable and/or complete data.
- Decision to modify the developmental plan of the drug.
- A decision on the part of the Sponsor to suspend or discontinue development of the drug.

The Sponsor reserves the right to discontinue the study for clinical or administrative reasons at any time. If the site does not recruit at a reasonable rate, the study may be discontinued at that site. Should the study be terminated and/or the site closed for whatever reason, all documentation and study drug pertaining to the study must be returned to the Sponsor or its representative, and the Investigators, IRB/IEC and Regulatory Authorities will be promptly informed of the termination and the reason for the decision. The Investigator should promptly inform the subjects and assure appropriate therapy and follow-up. Subjects should then be withdrawn from the study.

#### **4.6 Drug Accountability/Disposition of APR-548 Supplies**

The investigator or designee will maintain accurate records of receipt and the condition of the study drug supplied for this study, including dates of receipt. In addition, accurate records will be kept of when and how much study drug is dispensed and administered to

each subject in the study. Any reasons for departure from the protocol dispensing regimen must also be recorded.

At the completion of the study, there will be a final reconciliation of all study drugs.

#### **4.7 Inclusion Criteria**

1. Provision of signed and dated, written informed consent prior to any study specific procedures.
2. Documented diagnosis of *TP53*-mutant MDS, according to WHO criteria that is previously untreated and meets IPSS-R classification of intermediate, high, or very high risk disease, or *TP53*-mutant MDS that is relapsed and/or refractory to prior treatments. Eligible *TP53* mutations are defined in [Appendix VII](#).
3. Adequate organ function as defined by the following laboratory values:
  - a. Creatinine clearance  $\geq 60$  mL/min (by Cockcroft-Gault method, [Appendix I](#)),
  - b. Total serum bilirubin  $\leq 1.5 \times$  upper limit of normal (ULN), unless due to Gilbert's syndrome or MDS organ involvement,
  - c. Alanine aminotransferase (ALT) and aspartate aminotransferase (AST)  $\leq 2.5 \times$  ULN, unless due to MDS organ involvement.
4. Age  $\geq 18$  years at the time of signing the informed consent form.
5. Eastern Cooperative Oncology Group (ECOG) performance status of 0, 1 or 2 ([Appendix II](#)).
6. Projected life expectancy of  $\geq 12$  weeks.
7. Clear ocular media and adequate pupil dilation to permit fundus examination and retinal imaging.
8. Female subjects must be surgically sterile, postmenopausal (for at least 1 year), or have negative results for a pregnancy test at screening, on a serum or urine sample obtained within 7 days prior to initiation of study treatment.
9. Heterosexual female subjects of childbearing potential must agree to use adequate contraception or practice sexual abstinence as the preferred and usual lifestyle of the subject during the study and for up to 90 days after study treatment discontinuation. Adequate contraception is defined by the concomitant use of 2 effective methods of contraception, which can be comprised of two barrier methods, or a barrier method plus a hormonal method or an intrauterine device that meets  $<1\%$  failure rate for protection from pregnancy in the product label ([Appendix III](#)). Females of non-childbearing potential are those who are postmenopausal greater than 1 year or who have had a bilateral tubal ligation or hysterectomy or bilateral oophorectomy. Female subjects must refrain from egg cell donation while on study treatment and for at least 90 days after the last dose of APR-548 or azacitidine, whichever is longer.
10. Male subjects with female partners of childbearing potential must have had a prior vasectomy or agree to use an adequate method of contraception (i.e., double barrier method: condom plus spermicidal agent) starting with the first dose of study therapy through 90 days after the last dose of APR-548 or azacitidine, whichever is longer. Male

subjects should agree to refrain from sperm donation during the study and for at least 90 days after the last dose of APR-548 or azacitidine, whichever is longer. Should a female partner of a male subject become pregnant or suspect she is pregnant while participating in the study, he should inform his treating physician and the female partner should contact her physician immediately.

#### **4.8 Exclusion Criteria**

1. Any of the following cardiac abnormalities:
  - a. Myocardial infarction within six months prior to enrollment;
  - b. New York Heart Association Class III or IV heart failure ([Appendix IV](#)) or known left ventricular ejection fraction <40%;
  - c. A history of familial long QT syndrome;
  - d. Symptomatic atrial or ventricular arrhythmias not controlled by medication(s);
  - e. QTcF  $\geq$ 470 msec, unless due to underlying bundle branch block and/or pacemaker and with the approval of the Medical Monitor.
2. Concomitant malignancies or previous malignancies with less than a 1-year disease-free interval at the time of signing informed consent. Subjects with adequately treated basal or squamous cell carcinoma of the skin, or adequately treated carcinoma *in situ* (e.g., cervix) may enroll irrespective of the time of diagnosis. Subjects with controlled, advanced prostate cancer are permitted.
3. Known hypersensitivity to mannitol.
4. Known hypersensitivity to fluorescein sodium.
5. Use of cytotoxic chemotherapeutic agents, or experimental agents for the treatment of *TP53*-mutant MDS within 14 days or 5 half-lives of the product (whichever is shorter) of the first day of study drug treatment.
6. Prior exposure to eprenetapopt (APR-246).
7. Ongoing or prior history of ocular or hepatic graft-versus-host disease following allogeneic SCT. Subjects receiving systemic immunosuppressive therapy for treatment of (not prophylaxis) of graft-versus-host disease must be off systemic immunosuppressive therapy for a minimum of 6 weeks.
8. A female subject who is pregnant or breast-feeding.
9. Known history of human immunodeficiency virus, active hepatitis B or active hepatitis C infection.
10. Malabsorption syndrome or other condition likely to affect gastrointestinal absorption of APR-548.
11. Known history or current evidence of ocular disease in either eye that, in the opinion of the investigator, may confound retinal assessments (e.g., glaucoma, advanced age-related macular degeneration, diabetic retinopathy, uveitis, or the presence of any condition that precludes adequate visualization of the fundus such as dense cataracts or

corneal scarring).

12. Family history of Leber hereditary optic neuropathy, autosomal dominant optic atrophy, late-onset retinal degeneration, familial dysautonomia or other hereditary mitochondrial disease, unless the causative mutation(s) in the family have been determined and the participant has tested negative for the mutation(s).
13. Known prior or current retinal or optic nerve disease (e.g., retinitis pigmentosa, diabetic retinopathy, optic neuritis) that could impact interpretation of new onset retinal or optic nerve disease.
14. Corrected visual acuity worse than 20/40.
15. Other severe acute or chronic medical or psychiatric condition or laboratory abnormality that, in the opinion of the investigator, may increase the risk associated with study participation or study treatment administration or may interfere with the interpretation of study results and/or would make the subject inappropriate for enrollment into this study.
16. Active uncontrolled infection.

#### **4.9 Inclusion of Women, Minorities and Children**

Both men and women  $\geq 18$  years of age and members of all races and ethnic groups are eligible for this study. Children are not eligible for this study because the safety and tolerability of the proposed dosing schedule has not been determined in adults.

#### **4.10 Withdrawal Criteria**

Protocol therapy can continue for subjects receiving clinical benefit, unless one or more study treatment discontinuation criteria are met, or at the subject's discretion, or if the study is terminated. Subjects are free to discontinue treatment or withdraw from the study at any time and for any reason, without penalty to their continuing medical care. Any discontinuation of treatment or withdrawal from the study must be fully documented in the eCRF and should be followed up by the investigator. The investigator may withdraw a subject at any time if this is considered to be in the subject's best interest.

##### **4.10.1 Study Treatment Discontinuation**

Study treatment must be discontinued if:

- Evidence of disease progression according to IWG 2006 criteria. Subjects who have PD but who are continuing to derive clinical benefit in the opinion of the investigator may continue to receive study treatment.
- A female subject becomes pregnant.
- A subject is non-compliant with the requirements of the protocol.
- A subject has an adverse experience that would, in the investigator's judgment, make continued participation in the study an unacceptable risk.
- The subject starts new treatment for their disease under study.

- The subject receives HSCT.

#### **4.10.2 Subject Withdrawal from Study Treatment**

If the subject is permanently withdrawn from study treatment, but does not withdraw consent from the study, the investigator should make every effort to have the subject complete all withdrawal assessments at the time of withdrawal and complete all scheduled follow-up visits.

#### **4.10.3 Study Completion**

Subject must be taken off the study if:

- The subject dies during the study.
- The subject is lost to follow-up.
- The subject withdraws consent for study participation.

#### **4.10.4 Subject Withdrawal from Study**

A subject may voluntarily withdraw from study treatment or withdraw consent from study participation at any time. The investigator may also, at his or her discretion, discontinue a subject from study treatment at any time. The investigator and/or designated staff will record the date and the reason for subject withdrawal from the study.

#### **4.10.5 Withdrawn Subjects**

When a subject is removed from the study treatment, the investigator will clearly document the reason in the medical record and complete the appropriate eCRF page describing the reason for discontinuation. In addition, every effort should be made to complete the appropriate assessments listed in Section [6.8](#).

Subjects who miss  $\geq 25\%$  of APR-548 doses for a nonmedical reason (e.g., subject's preference) or noncompliance will be replaced.

### **4.11 Noncompliance**

All instances of protocol deviations will be recorded according to guidelines per Sponsor's representative.

## **5.0 TREATMENT OF SUBJECTS**

### **5.1 Drug Preparation and Administration**

Study treatment may be administered on an outpatient basis. No investigational or commercial agents or therapies other than those described below may be administered with the intent to treat the subject's disease.

### 5.1.1 APR-548

The APR-548 starting dose is 50 mg/day administered p.o during Days 1–4 for the 28-day safety run-in and in the 28-day cycles in the combination portion.

APR-548 is distributed to sites as a powder in bottle for oral solution. APR-548 should be reconstituted with cold sterile water as follows:

- 150 mg bottle once reconstituted with 30 mL of cold sterile water will be 5 mg/mL.
- 150 mg bottle once reconstituted with 10 mL of cold sterile water will be 15 mg/mL.
- 300 mg bottle once reconstituted with 10 mL of cold sterile water will be 30 mg/mL.

The prepared solution should be taken with an additional 200 mL of water at least 2 hours after and 1 hour before any food intake.

Detailed instructions on vial concentration, preparation and dispensing can be found in the Pharmacy Binder.

### 5.1.2 Azacitidine

Azacitidine is given at the standard dose of 75 mg/m^2 s.c. or i.v. over 7 consecutive days, Days 1 – 7. Cycles should be repeated every 28 days. S.c. route is preferred but i.v. is allowed at the investigator's discretion. The same route should be maintained over the 7-day treatment period (whichever route of administration is used on Day 1; the same route should be followed on all other days). On days of concomitant APR-548 intake, azacitidine should be administered 1 hour ( $\pm$ 15 min) after APR-548. Detailed instructions on preparation and administration can be found in the current United States Prescribing Information (USPI). Missed doses, such as for a weekend or holiday, for any reason but toxicity may, at the investigator's decision, be replaced by adding an additional dosing day for azacitidine so that the subject receives the total 7 days of treatment per cycle. If the azacitidine dose interruption is >3 days, discuss with the Medical Monitor.

### 5.1.3 Dose-Limiting Toxicity

All treatment-emergent adverse events (TEAEs) are relevant to the determination of DLTs unless they are clearly and solely due to the disease under study. During the 28-day safety run-in period for APR-548 monotherapy and during the 28-day safety run-in period for APR-548 in combination with azacitidine, a DLT is defined as any of the following TEAEs defined by the National Cancer Institute Common Terminology Criteria for Adverse Events (NCI-CTCAE) version 5.0, as follows:

- Non-hematological NCI-CTCAE  $\geq$ Grade 3 AE, including ocular AEs that are different from retinopathy or optic nerve disorder classifications.
- Prolonged myelosuppression with the persistence of  $\geq$ Grade 4 neutropenia or thrombocytopenia in the absence of disease lasting 14 days from the initial

administration of APR-548 (only during the safety run-in period for APR-548 monotherapy).

- Grade 3 nausea/vomiting/diarrhea/fatigue/CNS AE. Grade 3 nausea/vomiting/diarrhea may be excluded if parenteral nutrition, tube feeding, or prolonged hospitalization is not required.
- New or worsening retinopathy or optic nerve disorder AE of any grade.
- Grade 3 metabolic/electrolyte abnormalities that do not resolve to  $\leq$ Grade 1 or baseline within 72 hours.
- Grade  $\geq$ 4 neutropenia lasting past day 28 in the absence of disease.
- Any AE, regardless of the NCI-CTCAE Grade, resulting in discontinuation, dose reduction or treatment with less than 75% of planned doses of APR-548, unless clearly and solely related to disease under study.

Investigator should contact the Medical Monitor to discuss any findings suggestive of ocular-associated AEs. Any  $\geq$ Grade 2 ocular-associated AEs are considered AEs of special interest and should be reported as SAEs. Subjects with signs and/or symptoms of vision changes should be seen immediately by ophthalmologist/retinal specialist. APR-548 may be permanently discontinued, following a discussion with the Medical Monitor, if:

- Any retinopathy or optic nerve disorder develops, regardless of perceived attribution to study drug, and
- A clinical retina specialist or ophthalmologist determines a retinal or optic nerve finding is substantially changed from the subject's baseline test.

Additionally, TEAEs that meet the above criteria, but occur after the DLT evaluation periods will not be defined as DLTs, but will be reported as AEs/SAEs and will be reviewed across all cohorts during the study to help determine the AE profile for the respective treatment regimens under study. A subject that discontinues APR-548 therapy during the DLT assessment period without DLT is considered evaluable for the purpose of safety only if at least 75% of the scheduled dose of APR-548 was administered in the monotherapy safety run-in period.

The DRT also will review any other emergent toxicities that are not explicitly defined by the DLT criteria to determine if any warrant a DLT designation.

#### **5.1.4 Dose Escalation Strategy**

The RP2D of APR-548 will be defined as the lowest dose of APR-548 that results in:

1. The mBED in the monotherapy safety run-in,
2. The dose that achieves the pre-defined level of maximum exposure in the monotherapy or combination therapy safety run-ins, or
3. The dose at which there are  $<2$  DLTs in 3-6 subjects in a cohort, in the monotherapy or combination therapy safety run-ins.

Up to 10 subjects may be enrolled at the RP2D per decision of the DRT to gain additional confidence in the RP2D.

DRT consisting of the Medical Monitor, Site Principal Investigators, independent retina specialist and other clinical research personnel that the Sponsor may deem appropriate, will hold data review meetings (DRMs) on an interim basis at a frequency dependent on study accrual. At these meetings, the DRT will review AEs and DLTs and make recommendations regarding the dose for the next dosing cohort and decide when the RP2D is reached.

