During the safety run-in of the monotherapy and during the safety run-in of the combination treatment, each subject within the dose level will be evaluated for safety and tolerability of APR-548. APR-548 dose escalation will be guided by an assessment of safety, PK and PD data, and may proceed until DLTs are observed or the pre-defined maximum exposure of APR-548 in plasma (average Cmax and AUC 8 µM and 16 µM·h, respectively) is reached, or the minimum biologically effective dose (mBED) is achieved (the dose at which no further incremental effect on markers of apoptosis and/or proliferation is observed, in the monotherapy safety run-in only). The DRT, consisting of the Medical Monitor, Site Principal Investigators, retina specialist and other clinical research personnel that the Sponsor deems appropriate, will review available PK, PD and safety data for each 3-6 subject cohort in both the safety run-in for the monotherapy and the combination portions, and increases in dose will be guided by the observed safety, PK and PD data, until the RP2D is determined. The RP2D of APR-548 will be defined as the lowest of:

1. mBED in the monotherapy safety run-in,
2. The dose that achieves the pre-defined level of maximum exposure in the monotherapy or combination therapy safety run-ins, or
3. The dose at which there are <2 DLTs in 3-6 subjects in a cohort, in the monotherapy

or combination therapy safety run-ins.

Up to 10 subjects may be enrolled at the RP2D per decision of the DRT to gain additional confidence in the RP2D.

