Subjects in Cohort 1 will receive a starting dose of 50 mg/day (Dose level 1). If there is a DLT in  $\leq 1/3$  subjects in Cohort 1, Cohort 1 will be expanded to enroll 3 more subjects. If  $\geq 2$  subjects out of the total 3-6 subjects have a DLT, dose escalation will not occur. If  $\leq 1$  DLT occurs in the 6 subjects treated at that dose level, the subsequent subject group (Cohort 2) will be enrolled upon DRT review of data as described above, at the APR-548 dose of 150 mg/day (Dose level 2). If  $\geq 2$  of 6 subjects at a dose level have a DLT, or if the pre-defined maximum exposure of APR-548 in plasma is reached or the mBED is achieved (in monotherapy safety run-in only), then dose escalation ceases. This study will evaluate up to 6 dose levels. Any subsequent dose escalation will not exceed 100% and will follow the same principle as described above. The table below shows the planned dose levels based on the expected APR-548 human PK and under the assumption that the doses are well tolerated. Once the RP2D is established, if only 3 subjects were treated at the RP2D, an additional 3 subjects will be included in the cohort and if  $\leq 1$  DLT occurs in the 6 subjects treated at that dose level, the RP2D will be defined.

The [REDACTED]

[REDACTED]

[REDACTED]

[REDACTED]

The DRT will also review any other emergent toxicities that are not explicitly defined by the DLT criteria to determine if any warrant a DLT designation.

If the dose escalation of the 28-day safety run-in proceeds more rapidly than the combination portion such that the dose of APR-548 undergoing evaluation in the 28-day safety run-in exceeds that being assessed in the combination portion, the subject will receive the dose of APR-548 currently being assessed for safety in the combination portion. If a subject in the 28-day safety run-in period has a dose reduction of APR-548 due to AE, the subject will proceed with Cycle 1 of the combination portion with the reduced dose of APR-548 in combination with standard dose azacitidine.

Following discussions with the DRT, the schedule of APR-548 may be modified, including multiple daily and weekly doses, based on available PK, PD, and safety data.

Subjects in the 28-day safety run-in period and in Cycle 1 of the combination portion who miss  $\geq 25\%$  of APR-548 doses for a nonmedical reason (e.g., subject's preference) or noncompliance will be replaced.

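### The RP2D definition leaves *highest* out of its tolerability item, and Section 5.1.4 read literally returns 50 mg/day once that dose is tolerated

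*Combined protocol and SAP*

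**What the plan says.** The RP2D definition is given in the Synopsis under Study Design, Treatment Plan and Statistics, and again in Sections 4.1 and 5.1.4. It has three items: the minimum biologically effective dose (mBED) from the monotherapy run-in, the dose reaching the exposure cap, and a tolerability item.

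- In Section 4.1 the lead-in is "The RP2D of APR-548 will be defined as the lowest of", and the tolerability item begins "The dose at which there are <2 DLTs in 3-6 subjects in a cohort, in the monotherapy". The three Synopsis copies have the same lead-in and the same item.
- In Section 5.1.4 the lead-in is instead "The RP2D of APR-548 will be defined as the lowest dose of APR-548 that results in". The tolerability item is unchanged and ends "DLTs in 3-6 subjects in a cohort, in the monotherapy or combination therapy safety run-ins".

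The surrounding text describes escalation past tolerated doses. In Section 4.1, "increases in dose will be guided by the observed safety, PK and PD data, until the RP2D is determined". Section 5.1.4 itself ends by having the DRT "make recommendations regarding the dose for the next dosing cohort and decide when the RP2D is reached". Section 4.1 moves from 50 to 150 mg/day once at most 1 of 6 subjects has a DLT, and states "This study will evaluate up to 6 dose levels". If only three subjects were treated at the RP2D, three more are added; when at most one "DLT occurs in the 6 subjects treated at that dose level, the RP2D will be defined".

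**The concern.** Item 3 gives the condition for any tolerated dose. In a 3+3 escalation every cleared level satisfies it, so the item describes a set of doses where the definition needs one. The Section 5.1.4 lead-in then asks for the lowest dose meeting any item, and the lowest member of that set is always the starting dose. That contradicts the escalation plan, in which tolerating 50 mg/day is the reason to go higher.

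The RP2D is primary endpoint 3 (Section 8.3.1) and fixes the dose at which up to 10 more subjects may be enrolled. A reader of the final report should be able to take the cohort data, apply the stated rule and arrive at the reported RP2D. With this text, the five copies do not yield one answer.

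There is also a gap in the wording on run-ins. Item 3 accepts a result from the monotherapy *or* the combination run-in. It does not say which governs when they differ, although the two run-ins have separate stopping rules.

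**Working it through.** **Inputs**

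- Planned doses: 50, 150 and 300 mg/day, with 450 mg/day only if updated PK allows it (Synopsis, Treatment Plan table).
- A level is cleared with at most 1 DLT in 6 subjects; up to 6 levels (Section 4.1).
- Exposure cap: average AUC 16 h·µM. Expected AUC at 300 mg/day: 16 h·µM (Synopsis, Treatment Plan table).
- Sample size: 6 escalation cohorts of 6, plus 10 at the RP2D (Synopsis, Statistics).
- DLT counts and rates below are assumed; the documents give none.

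**Plan's own figure.** 6 × 6 + 10 = 46, as stated.

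**Step 1: how many doses item 3 names.** Each cleared level has fewer than 2 DLTs, so after k cleared levels item 3 names k doses.

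- 50 cleared: {50}, 1 dose
- 50 and 150 cleared: {50, 150}, 2 doses
- 50, 150 and 300 cleared: {50, 150, 300}, 3 doses
- Ceiling under the six-level maximum: 6 doses

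On expected PK the exposure cap is met at the third level, so counts above 3 require observed exposure below expectation.

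**Step 2: worked example.** Assume 0/6, 1/6 and 2/6 DLTs at 50, 150 and 300 mg/day, the same in both run-ins, with the mBED not reached.

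- Item 2 candidate: 300 mg/day (expected AUC 16 against a cap of 16).
- Doses meeting item 3: {50, 150}.
- Section 5.1.4 read literally: min{50, 150, 300} = 50 mg/day.
- Lowest of three ceilings, with item 3 as the highest tolerated dose: min(300, 150) = 150 mg/day.
- The other four copies: no answer, because item 3 could be 50 or 150.

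If 300 mg/day did not reach the cap, item 2 would drop out and the answers would still be 50 and 150.

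**Step 3: other assumed sequences, item 3 alone (items 1 and 2 not reached)**

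| DLTs out of 6, by dose (mg/day) | Lowest dose with <2 DLTs | Highest dose with <2 DLTs |
|---|---|---|
| 0, 0, 0, 2 at 50, 150, 300, 450 | 50 | 300 |
| 1, 0, 1 at 50, 150, 300 | 50 | 300 |
| 0, 2 at 50, 150 | 50 | 50 |

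The readings agree only when 50 mg/day is the sole tolerated dose.

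**Step 4: how often the literal reading would point to 50 mg/day.** This happens whenever 50 mg/day has fewer than 2 DLTs in 6. With true DLT rate p, the probability is (1−p)^6 + 6p(1−p)^5. At p = 10%: 0.5314 + 0.3543 = 0.8857.

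| Assumed p at 50 mg/day | P(<2 DLTs in 6) |
|---|---|
| 1% | 99.9% |
| 5% | 96.7% |
| 10% | 88.6% |
| 20% | 65.5% |
| 33% | 35.8% |

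These describe the text, not the DRT's likely behaviour.

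**Step 5: the two run-ins.** Assume 150 mg/day has 1/6 DLTs in monotherapy and 2/6 in combination. The monotherapy result is below 2, so item 3 is met through the *or*, although the combination result stops combination escalation.

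**The case against.** The strongest reply is that nobody would read the protocol this way. The Section 5.1.4 sentence is ungrammatical, since a dose cannot result in a dose, and looks like a garbled form of the lead-in used in the other four copies. The Synopsis names a standard 3+3 design. Escalation stops at the earliest of the mBED, two or more DLTs, or the exposure limit. Cohort 2 would have no purpose if a tolerated 50 mg/day were already the RP2D. Taken together, these point to one rule: the lowest of three ceilings, with item 3 as the highest tolerated dose.

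The intent can indeed be inferred, and no selection of 50 mg/day is predicted. But the provisions cited say when to escalate, when to stop and how to confirm a dose already picked. None says which cleared dose is the RP2D. Correcting the Section 5.1.4 lead-in alone would still leave item 3 without a unique dose in all five copies.

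It may also be said that Figure 1, which is not shown, or the redacted parts of Sections 2.5, 2.7 and 4.1 could supply the missing word. That cannot be excluded for item 3. It would not repair the Section 5.1.4 lead-in, which is visible and differs from the other copies.

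On the run-ins, a reader who already supplies *highest* may well take the lower of the two results. That is a second inference the text does not state, and it bears on the dose given with azacitidine.

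**Conclusion.** The concern holds. Item 3 lacks *highest* in all five copies, and the Section 5.1.4 lead-in differs from the other four in a way that, read literally, returns 50 mg/day whenever that dose is tolerated. In the worked example the gap is 50 against 150 mg/day. In general, item 3 names as many doses as have been cleared, where one is needed.

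This is an error in the written definition of a primary endpoint and should be corrected. No harm rate is claimed, and the DRT would probably act on the evident intent. The DLT counts and rates are illustrative, and the item 2 candidate relies on the protocol's expected PK. The textual finding depends on neither. The one open point is whether unseen material clarifies item 3.

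**What to change.** 1. In Section 5.1.4, replace the lead-in with the one used in Section 4.1: "The RP2D of APR-548 will be defined as the lowest of".
2. In all five copies (Synopsis Study Design, Treatment Plan and Statistics; Sections 4.1 and 5.1.4), insert *highest* before *dose* in item 3.
3. At the end of item 3 in each copy, add: *taking the lower of the monotherapy and combination run-in results*.
4. Leave Section 4.1's expansion to six subjects, with at most one DLT, as the confirmation step. Item 3 keeps its 3-6 subject range, so a three-subject cohort still depends on that step before the RP2D is final.

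The cost is protocol wording in five places. Cohort sizes and DLT thresholds do not change, and no subjects, visits or assessments are added.
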